## **6.3 Dose Adjustments**

**Adverse events** that are classified as unrelated or unlikely related do not require dose adjustment, and the prior dose can be resumed once the **adverse event** has resolved. For toxicities that are classified as possibly related to the AE, dose adjustment should be addressed as follows:

For patients who are escalated to 10 mg every two weeks, any toxicity  $\geq$  Grade 2 will result in an initial reduction to 5 mg every two weeks. If the grade of the toxicity is  $\leq$  grade 2 for all toxicities or  $\leq$  grade 3 for laboratory abnormalities other than hepatic, renal or hematologic, an increase in dose to the prior level can then occur after the toxicity has completely resolved and the 5 mg every two weeks dose has been shown to be tolerable. Patient may then receive either 10 mg every two weeks or 5 mg every week at the discretion of the investigator.

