### **6.3.1 Entinostat-Related Non Hematologic Toxicity**

The rules outlined in Table 6-1 are to be followed for the management of non-hematologic toxicities that are probably or definitely due to entinostat, with toxicities graded by the Investigator according to the NCI, CTCAE, version 4.03.

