**Table 6-1 Non-hematologic Toxicity: Dose Modifications for Entinostat**

Toxicity	Dose modifications
Grade 4	
Administer symptomatic remedies/ start prophylaxis.
 
Hold dose until recovery to Grade 1 or baseline under the following directions.
 
 
1. If recovered within 4 weeks of onset (i.e.: ≤3 missed doses) , resume study drug as follows: 
 
• If receiving 10 mg bi-weekly, restart study drug at 5 mg weekly.
 
• If receiving 5 mg, restart study drug at 3 mg
 
• If receiving 3 mg, restart study drug at 2 mg
 
• If receiving 2 mg, discontinue study treatment
 
 
 
2. If dose is held for 4 consecutive weeks, permanently discontinue study drug.
 

Grade 3	
Administer symptomatic remedies/ start prophylaxis. Hold dose until recovery to Grade 1 or baseline under the following directions:
 
 
1. If not recovered by next scheduled dose, skip the dose. If recovered by next scheduled dose, resume study drug at prior dose or per investigator's discretion.
 
2. If not recovered by either of the next 2 scheduled doses and receiving 2 mg, permanently discontinue study treatment. Otherwise, skip each dose and if recovered by the 4th dose, resume study drug as follows: 
 
• If receiving 10 mg bi-weekly, restart study drug at 5 mg weekly.
 
• If receiving 5 mg, restart study drug at 3 mg.
 
• If receiving 3 mg, restart study drug at 2 mg.
 
 
 
3. If dose is held for 4 consecutive weeks, permanently discontinue study drug.
 

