Recurrence of the same Grade 3 toxicity despite dose reduction	
If the same ≥Grade 3 event recurs:
 
 
1. Administer symptomatic remedies/ start prophylaxis. If receiving 2 mg, permanently discontinue study drug. Otherwise, hold dose until recovery to Grade 1 or baseline.
 
2. If recovered for either of the next 2 scheduled doses, resume study drug as follows: 
 
• If receiving 10 mg bi-weekly, restart study drug at 5 mg weekly.
 
• If receiving 5 mg, restart study drug at 3 mg
 
• If receiving 3 mg, restart study drug at 2 mg
 
 
 
3. If the same ≥Grade 3 event recurs (i.e., third occurrence) despite entinostat dose reduction to 2 mg, as described above, discontinue study drug.
 

≤Grade 2	
Administer symptomatic remedies / start prophylaxis.
 
Dosing of study drug may be interrupted at the Investigator's discretion, in consultation with the Medical Monitor.
 
 
• If dose is held for 4 consecutive weeks, permanently discontinue study drug.
 
• If toxicity resolves, resume entinostat at the original dose.
 

 If Entinostat dose is reduced, an increase in dose to prior level can occur only after the AE has completely resolved.

 If greater than 50% of doses are missed during any 6 week period, discontinue from study drug treatment.

**Please note:** Patients that do not require a dose reduction due to AE during the first treatment cycle should continue at 5mg weekly for at least one more cycle prior to changing to 10mg biweekly.

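### For patients escalated to 10 mg every two weeks, Section 6.3 halves the dose per cycle after toxicity, but three lines of Table 6-1 restart them with no cut per cycle

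*Combined protocol and SAP*

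**What the plan says.** Section 6.1 starts everyone on 5 mg weekly in a 28-day cycle and lets patients who tolerate it change to 10 mg every two weeks.

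Section 6.3 then sets a rule for the escalated patients only. Any toxicity of grade 2 or more "will result in an initial reduction to 5 mg every two weeks". A way back up is given for events no worse than grade 2, or no worse than grade 3 for laboratory findings outside the liver, kidney and blood counts. In those cases "an increase in dose to the prior level can then occur after the toxicity has completely resolved", provided that 5 mg every two weeks has also been tolerated. The patient may then take 10 mg every two weeks or 5 mg weekly, as the investigator chooses.

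Table 6-1 gives escalated patients their own instruction: "If receiving 10 mg bi-weekly, restart study drug at 5 mg weekly". It appears under grade 4, under grade 3 that does not recover promptly, and under recurrence of the same grade 3 event.

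Other lines do not name escalated patients. For grade 3 recovered by the next dose, Table 6-1 lets sites "resume study drug at prior dose or per" the investigator's judgment. For grade 2 or lower it says "If toxicity resolves, resume entinostat at the original dose". Table 6-2 resumes the prior dose after prompt hematologic recovery and has no step from 10 mg in its other branches.

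The lead-ins differ on attribution. Section 6.3 begins "For toxicities that are classified as possibly related to the AE", while Section 6.3.1 applies Table 6-1 to "non-hematologic toxicities that are probably or definitely due to entinostat".

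**The concern.** Two texts, each written for escalated patients, give different restart doses after the same event. A site following Section 6.3 halves the dose per cycle. A site following Table 6-1 keeps the cycle total and only splits it into smaller, more frequent doses. Each site could point to protocol text in its support, and no precedence is stated.

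The stake is patient safety and consistency. Up to four centers take part (Section 3.2). Section 11.4 sets no formal stopping rule for safety, so the individual dose rules are a main protection. The lines concerned include grade 4 non-hematologic events. Mixed practice would also blur the exposure and toxicity summaries for escalated patients and leave monitors without one standard for treatment compliance.

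**Working it through.** The plan states no dose per cycle, so there is no figure to reproduce. Dose per cycle = mg per dose × doses in 28 days, with 4 doses if weekly and 2 if every two weeks.

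- Starting regimen, 5 mg weekly (Section 6.1): 5 × 4 = 20 mg.
- Escalated regimen, 10 mg every two weeks (Section 6.1): 10 × 2 = 20 mg.
- Section 6.3 restart, 5 mg every two weeks: 5 × 2 = 10 mg, a cut of (20 − 10)/20 = 50%.
- Table 6-1 restart, 5 mg weekly: 5 × 4 = 20 mg, a cut of (20 − 20)/20 = 0%.
- Ratio of the two restarts: 20/10 = 2.

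These are the recovery branches that a patient on 10 mg every two weeks can meet. Section 6.3 gives 10 mg per cycle in each of them if the event is of grade 2 or more.

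| Branch | Table restart | mg per cycle | Reading against Section 6.3 |
|---|---|---|---|
| 6-1, grade 4 | 5 mg weekly | 20 | explicit conflict |
| 6-1, grade 3, slow recovery | 5 mg weekly | 20 | explicit conflict |
| 6-1, same grade 3 recurring | 5 mg weekly | 20 | explicit conflict, rarely reached |
| 6-1, grade 3, prompt recovery | prior dose or discretion | 20 if prior dose | reconcilable, since 6.3 can be followed |
| 6-1, grade 2 | original dose | 20 | ambiguous |
| 6-2, prompt recovery | prior dose | 20 | ambiguous |
| 6-2, slower recovery | no step from 10 mg | none | gap that 6.3 fills |
| 6-2, recurrence | no step from 10 mg | none | gap that 6.3 fills |

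The count is 3 explicit conflicts + 1 reconcilable + 2 ambiguous + 2 gaps = 8.

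Two points bear on the explicit lines. First, Section 6.3 treats 5 mg weekly as one of the two doses a patient may return to, after a lower-grade event, full resolution and proven tolerance of 5 mg every two weeks. Table 6-1 moves a patient with a grade 4 event straight to that dose. Second, Section 6.3 states no route back after grade 4, and after grade 3 only for the laboratory findings noted above, so under that section the lower dose is not just an interim step. Footnote 1 of both tables says that "an increase in dose to prior level can occur only after the AE has completely resolved". It does not mention the grade limit or the tolerance condition of Section 6.3.

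**The case against.** **Attribution.** Read literally, Section 6.3 covers possibly related events and Table 6-1 probably or definitely related ones, so the two would never meet. That reading is available on the words. But it would halve the cycle dose for a possibly related grade 2 event and leave it uncut for a definitely related grade 4 event, which is the wrong way round. The Section 6.3 lead-in is also garbled, since it relates toxicity to the adverse event rather than to the drug, so it is weak evidence of a deliberate split. For Table 6-2, the heading of Section 6.3.2 says entinostat-related but sets no degree of certainty.

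**Number of conflicts.** A reader might infer five or more conflicts by adding the grade 2 row of Table 6-1 and the prompt-recovery line of Table 6-2. The documents do not support that. Both lines are generic, and Section 6.3, as the rule specific to escalated patients, can be read to override them, just as it fills the gaps elsewhere in Table 6-2. The original dose in the grade 2 row is not defined, and Section 6.3 itself allows return after grade 2. This part of the objection stands. So does the remark that the recurrence line is narrow: it applies after a dose reduction, so a patient must have gone back up to 10 mg every two weeks to meet it.

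**Harm.** In the three explicit lines the single dose falls from 10 to 5 mg under either rule. Section 2.4 reports 5 mg weekly and 10 mg every other week as well tolerated in combination regimens. Table 6-1 holds drug until recovery to grade 1 or baseline. These points limit the harm and stand. They do not make the rules agree, and Section 2.4 also reports a half-life of 40 to 120 hours with drug detectable at 168 hours, so the interval and the cycle total both matter to exposure.

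**Conclusion.** Wrong as written. Section 6.3 and three explicit lines of Table 6-1 prescribe restart doses of 10 and 20 mg per cycle for the same escalated patients. Grade 4 and slowly recovering grade 3 are the lines that matter in practice. The two generic lines are ambiguous rather than contradictory.

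This rests on reading the Section 6.3 lead-in as at least possibly related, and on the absence of any precedence statement. The number of patients affected cannot be computed, because the documents give neither an escalation rate nor a toxicity rate.

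Two stronger inferences should be resisted. A reader might conclude that the tables overdose patients, but no branch exceeds the 20 mg per cycle at which everyone starts. A reader might also conclude that the efficacy design is compromised. It is not: the Simon stage sizes and response cut-offs do not depend on these rules, and Section 11.5 counts completed cycles toward evaluability whatever the dose. This is a contradiction between dosing rules that should be corrected, with limited reach.

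**What to change.** In the three Table 6-1 lines, change the restart dose for patients on 10 mg every two weeks from 5 mg weekly to 5 mg every two weeks, the more protective rule already in Section 6.3. If the clinical team documents that 5 mg weekly was intended, amend Section 6.3 to match instead.

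Add one statement to both tables: for escalated patients, Section 6.3 governs the restart dose and any return to the prior level after a grade 2 or higher event that is at least possibly related. This settles the two ambiguous lines and the Table 6-2 gaps. It also makes plain that the discretion in the prompt-recovery grade 3 line does not displace Section 6.3 for these patients.

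Leave the hold and discontinuation rules unchanged, and change nothing for patients on 5 mg weekly. Do not add 3 mg or 2 mg every-two-week levels, which appear nowhere in the protocol.

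The cost is an amendment with IRB approval at up to four centers, and slightly lower exposure in escalated patients who have toxicity (10 instead of 20 mg per cycle until Section 6.3 allows return, where it does). Sample size, decision rule and evaluability stay as they are.

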### **6.3.1 Entinostat-Related Non Hematologic Toxicity**

The rules outlined in Table 6-1 are to be followed for the management of non-hematologic toxicities that are probably or definitely due to entinostat, with toxicities graded by the Investigator according to the NCI, CTCAE, version 4.03.

**Table 6-1 Non-hematologic Toxicity: Dose Modifications for Entinostat**

Toxicity	Dose modifications
Grade 4	
Administer symptomatic remedies/ start prophylaxis.
 
Hold dose until recovery to Grade 1 or baseline under the following directions.
 
 
1. If recovered within 4 weeks of onset (i.e.: ≤3 missed doses) , resume study drug as follows: 
 
• If receiving 10 mg bi-weekly, restart study drug at 5 mg weekly.
 
• If receiving 5 mg, restart study drug at 3 mg
 
• If receiving 3 mg, restart study drug at 2 mg
 
• If receiving 2 mg, discontinue study treatment
 
 
 
2. If dose is held for 4 consecutive weeks, permanently discontinue study drug.
 

Grade 3	
Administer symptomatic remedies/ start prophylaxis. Hold dose until recovery to Grade 1 or baseline under the following directions:
 
 
1. If not recovered by next scheduled dose, skip the dose. If recovered by next scheduled dose, resume study drug at prior dose or per investigator's discretion.
 
2. If not recovered by either of the next 2 scheduled doses and receiving 2 mg, permanently discontinue study treatment. Otherwise, skip each dose and if recovered by the 4th dose, resume study drug as follows: 
 
• If receiving 10 mg bi-weekly, restart study drug at 5 mg weekly.
 
• If receiving 5 mg, restart study drug at 3 mg.
 
• If receiving 3 mg, restart study drug at 2 mg.
 
 
 
3. If dose is held for 4 consecutive weeks, permanently discontinue study drug.
 

Recurrence of the same Grade 3 toxicity despite dose reduction	
If the same ≥Grade 3 event recurs:
 
 
1. Administer symptomatic remedies/ start prophylaxis. If receiving 2 mg, permanently discontinue study drug. Otherwise, hold dose until recovery to Grade 1 or baseline.
 
2. If recovered for either of the next 2 scheduled doses, resume study drug as follows: 
 
• If receiving 10 mg bi-weekly, restart study drug at 5 mg weekly.
 
• If receiving 5 mg, restart study drug at 3 mg
 
• If receiving 3 mg, restart study drug at 2 mg
 
 
 
3. If the same ≥Grade 3 event recurs (i.e., third occurrence) despite entinostat dose reduction to 2 mg, as described above, discontinue study drug.
 

≤Grade 2	
Administer symptomatic remedies / start prophylaxis.
 
Dosing of study drug may be interrupted at the Investigator's discretion, in consultation with the Medical Monitor.
 
 
• If dose is held for 4 consecutive weeks, permanently discontinue study drug.
 
• If toxicity resolves, resume entinostat at the original dose.
 

 If Entinostat dose is reduced, an increase in dose to prior level can occur only after the AE has completely resolved.

 If greater than 50% of doses are missed during any 6 week period, discontinue from study drug treatment.

**Please note:** Patients that do not require a dose reduction due to AE during the first treatment cycle should continue at 5mg weekly for at least one more cycle prior to changing to 10mg biweekly.

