### **6.1 Entinostat Administration**

The starting dose of entinostat will be 5 mg administered orally every week (days 1, 8, 15, and 22) of a 28 day treatment cycle. The dose may be changed from 5 mg weekly to 10 mg every two weeks after cycle 1 for patients who have not experienced treatment-related adverse events (excluding manageable events) with severity grade  $\geq 2$  (moderate). Provisions for dose reductions are described in Section 6.3.

Entinostat is supplied in 5 mg (intense yellow in color) and 1 mg (light brown in color) coated tablets. Study drug should be taken in the morning. Tablets should be taken on an empty stomach, at least 2 hours after a meal and at least 1 hour before the next meal.

Tablets should be taken whole and not crushed. If a patient vomits after taking a dose of medication, dosing should not be re-administered but instead the dose should be skipped. If the patient inadvertently missed the dose on scheduled day, the dose could be taken within 2 days of the scheduled dose. However, all efforts should be made to adhere to dosing schedule.

Procedures for dose reductions and delays due to toxicity are summarized in Section 6.3. In the event of necessary dose reductions, each study site pharmacy will be supplied with 1.0 mg tablets in addition to the 5.0 mg tablets.

Unused tablets or empty bottles will be returned to the clinic for accountability purposes.

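### Table 6-1, Grade 3 row: for patients on 10 mg every two weeks, the restart window runs past the 4-week discontinuation limit, and no line says which rule prevails

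*Combined protocol and SAP*

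**What the plan says.** Section 6.1 sets two dosing intervals. Treatment starts weekly: "The starting dose of entinostat will be 5 mg administered orally every week (days 1, 8, 15, and 22) of a 28 day treatment cycle". It may then move to a 14-day interval: "The dose may be changed from 5 mg weekly to 10 mg every two weeks after cycle 1".

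Table 6-1 governs holds for non-hematologic toxicity judged probably or definitely due to entinostat.

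- **Grade 3, step 2.** Once the next two scheduled doses have been missed, patients not already at 2 mg follow this line: "Otherwise, skip each dose and if recovered by the 4 th dose, resume study drug as follows". The list beneath it names the two-weekly group: "If receiving 10 mg bi-weekly, restart study drug at 5 mg weekly".
- **Grade 3, step 3.** "If dose is held for 4 consecutive weeks, permanently discontinue study drug". The same line appears in the Grade 4 and Grade 2-or-lower rows.
- **Grade 4, step 1.** Restart is allowed on this condition, with its own gloss in doses: "If recovered within 4 weeks of onset (i.e.: ≤3 missed doses".
- **Footnote 2.** "If greater than 50% of doses are missed during any 6 week period, discontinue from study drug treatment". In Table 6-1 its marker sits on the Grade 2-or-lower row.

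**The concern.** The table limits a hold in two units, calendar weeks and numbers of doses. The two agree only if the dosing interval is fixed, and Section 6.1 allows two intervals. Because the restart list names patients on 10 mg every two weeks, the table is clearly meant to cover them, yet its dose counts match 4 weeks only at a 7-day interval.

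Two sites could apply the same row to the same event and reach opposite, irreversible dispositions. The primary endpoint counts a response only if it is documented while the patient is on study drug (Section 11.2), so stopping treatment ends the chance to respond. Discontinuations for adverse events are also one of the inputs to ongoing safety review, for which Section 11.4 sets no formal stopping rule.

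**Working it through.** **Inputs.** Dosing interval d = 7 days (weekly) or 14 days (two-weekly), from Section 6.1. Discontinuation limit = 4 × 7 = 28 days, from Table 6-1.

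**The plan's own equation (Grade 4 row).** Let the next dose be due o days after onset. If dosing resumes on schedule no later than day 28, the number of missed doses is floor((28 − o)/d).

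- Weekly: o = 1 to 6 gives 3; o = 0 gives 4. The plan's figure of three is reproduced, except when onset falls on a dosing day.
- Two-weekly: o = 1 to 13 gives 1; o = 0 gives 2. The figure of three is not reproduced. Three missed two-weekly doses mean 3 × 14 = 42 days held if dosing resumes at the next slot, and the third missed dose itself already falls 2 × 14 = 28 days after the first.

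**Grade 3 row, step 2 against step 3.** The k-th scheduled dose from the start of the hold falls (k − 1) × d days after the first skipped dose, k × d days after the last dose taken, and between those two values after onset.

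| Restart at | Doses missed | Days from first skipped dose | Days from last dose taken | Days from onset |
|---|---|---|---|---|
| Weekly, 4th dose | 3 | 21 | 28 | 21–28 |
| Two-weekly, 3rd dose | 2 | 28 | 42 | 28–42 |
| Two-weekly, 4th dose | 3 | 42 | 56 | 42–56 |

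On two-weekly dosing, a restart at the 4th dose exceeds 28 days on every clock, and a restart at the 3rd dose meets or exceeds it. If the last dose taken is counted as dose 1, the 4th dose becomes the 3rd row-slot of the hold, which is still 28 days from the first skipped dose.

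**Illustration of the conflict.** Two-weekly doses are due on days 0 (first skipped), 14, 28 and 42, and the patient recovers on day 35. Step 2: the first two doses were missed and recovery came before the 4th, so restart at 5 mg weekly. Step 3: the hold reached 28 days on day 28, so discontinue permanently.

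**Illustration without conflict.** Same patient, recovery on day 20. Step 2 applies because doses on days 0 and 14 were missed. The restart is on a weekly schedule, and nothing says it must wait for day 28. If it happens promptly, the hold is about 20 days on this clock and step 3 is not reached.

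**Footnote 2.** Six weeks hold 42/7 = 6 weekly doses or 42/14 = 3 two-weekly doses. More than 50% missed means at least 4 of 6 weekly, but 2 of 3 (67%) two-weekly.

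**The case against.** The best answer is that the 4-week line is unconditional and recurs across the table, so it reads naturally as an outer cap on step 2. That would remove the conflict, but the table does not say it. On a two-weekly schedule the 4th-dose window would then never be reached, although step 2 offers it to exactly those patients. Step 2 would still need rewriting.

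Several limits on the point do stand.

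- A reader might infer that step 2 always conflicts with step 3 for two-weekly patients. That assumes the restart waits for a two-weekly slot. The restart is at 5 mg weekly, so a patient who recovers after the second skipped dose and restarts before day 28 can satisfy both steps when the hold is counted from the first skipped dose. On a last-dose clock the limit would arrive earlier (28 − 14 = 14 days after the first skipped dose) and the overlap would be wider, but the text does not adopt that clock.
- A reader might set 8 weeks (56 days, from the last dose taken) against the 4-week limit while calling weekly dosing consistent. That mixes clocks: from the last dose taken, the weekly 4th dose is itself at exactly 28 days. From the first skipped dose the comparison is 42 days with 21.
- A reader might infer a matching contradiction in the Grade 4 row. Its operative tests are both calendar limits of 4 weeks and roughly agree, and a two-weekly patient who recovers in time misses 1 to 2 doses, which satisfies three or fewer. Only the gloss misfits.
- A reader might treat footnote 2 as a further Grade 3 rule. Its marker in Table 6-1 does not put it there, so it is supporting evidence only.
- The recurrence row has no 4-week line and shows no such conflict.
- Affected patients will usually still be evaluable. Section 11.5 asks for two cycles at any dose plus two CT scans, and the note under Table 6-1 keeps patients on weekly dosing for at least one more cycle after the first.

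**Conclusion.** The point holds for the Grade 3 row. For patients on 10 mg every two weeks, recovery about 28 to 42 days after the first skipped dose leads to restart under step 2 and permanent discontinuation under step 3, with no stated precedence. This rests on counting the hold from the first skipped dose and counting that dose as the first of the four. Other clock starts move the edges of the window but do not bring a restart at the 4th two-weekly dose within 28 days. The Grade 4 parenthesis is a lesser misfit of units without a clear contradiction in disposition.

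The group is narrow: patients already switched to the two-weekly schedule, with a related non-hematologic Grade 3 event and a hold of roughly 4 to 6 weeks. The documents give no count, and it is probably small. A reader might infer a measurable distortion of the response rate; the documents provide nothing from which to estimate one. The first stage does turn on 2 responders among 9 patients (Section 11.3.1), so how a single patient is handled could matter, but that is a possibility and not a demonstrated effect. The case for acting is that a permanent-discontinuation rule should give one answer.

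**What to change.** Reconcile Grade 3 steps 2 and 3, and the Grade 4 parenthesis, separately for the weekly and two-weekly schedules. The revised table should:

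- express the hold limit in one unit, weeks or missed doses;
- state when the hold clock starts (first skipped dose, last dose taken or onset);
- state which line prevails when two apply;
- say whether a patient moving from two-weekly to weekly dosing may restart before the next two-weekly slot;
- say which rows footnote 2 governs.

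Which limit applies is a decision for the sponsor's clinical team, and no view is offered here. The cost is a wording amendment to one table, with no effect on sample size or analysis. The same amendment could reconcile a neighbouring mismatch: for patients on 10 mg every two weeks, Section 6.3 and Table 6-1 name different reduced schedules (5 mg every two weeks and 5 mg weekly).
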